9. STUDY DRUG MATERIALS AND MANAGEMENT

9.1. Study Drug Packaging and Labeling

Test and reference drugs will be packaged in bottles and labeled according to applicable regulatory requirements. The label for study drugs will include at least the following information:

- Name and address of sponsor
- Protocol number of other identifier to reference the study
- Storage conditions

The clinical site pharmacist or designee will prepare the study drug according to the randomization scheme, maintain the drug packaging and labeling log.

9.2. Study Drug Storage and Accountability

All investigational drug supplies will be stored in a secure, locked area, under the responsibility of the Investigator or other authorized individual.

The Investigator or designee must maintain accurate records of the receipt of all study drug, including date received, lot number, expiration date if applicable, amount received, condition of the package and the disposition of all study drug.

Current dispensing records will also be maintained including the date and amount of study drug dispensed and the identity of the subject receiving the study drug.

9.3. Study Drug Handling and Disposal

All unused study drug and supplies must be returned to CSPC Pharma or disposed according to sponsor's instruction after the study is completed and the drug accountability log is reconciled.

10. PHARMACOKINETICS ASSESSMENTS

Plasma concentrations of (S)amlodipine and (R)amlodipine will be measured with validated methods under GLP.

Guidelines for preparing, labeling, storing and shipping plasma samples for bioanalytical analyses will be provided in a separate manual.

10.1. Blood Sample Collection

A total of 23 blood samples will be collected at the following time points: within 30 min prior to dosing and at 1, 2, 3, 4, 5, 6, 7, 8, 9, 10, 11, 12, 14, 16, 24, 36, 48, 72, 96, 120, 144, and 168 hours after each dosing.

Contents of tube will be mixed thoroughly with gentle inversion (a minimum of 8 times) to mix the anti-coagulant. Total volume of blood collected for determination of study drug concentration will be approximately 100 mL ($16 \times 6mL$) for each subject.

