- 10. A positive result for alcohol or drugs of abuse at screening or admission;
- 11. Tobacco use within 6 months prior to screening;
- 12. An unwillingness or inability to comply with food and beverage restrictions during study participation;
- 13. Donation or blood collection of more than 1 unit (approximate 450 mL) of blood (or blood products) or acute loss of blood during the 90 days prior to screening;
- 14. Use of prescription or over-the-counter (OTC) medications, and herbal medicines (including St John's Wort, herbal teas, garlic extracts) within 14 days prior to dosing;
- 15. A history of suicide attempt in the past 12 months and/or seen by the investigator as having a significant history of risk of suicide or homicide;
- 16. A history of intolerance or hypersensitivity to amlodipine or any excipients;
- 17. An unwillingness of male participants to use appropriate contraceptive measures if engaging in sex intercourse with a female partner of childbearing potential during the study and 60 days after discontinuation of study treatment. Sexual intercourse with pregnant or lactating women is prohibited.

Duration of Study

The total duration of the study for each completed subject is about 2 months, including about 44 days for Part 1 (up to 21 days for screening, 14 days for Period One before cross-over and 9 days for Period Two after cross-over) and about 14 days for Part 2 (5 days before dosing and 9 days after dosing).

Statistical Methods

PK

All the PK parameters and baseline subject characteristics will be summarized using descriptive statistics. The following PK parameters for plasma (S)amlodipine and (R)amlodipine concentrations will be compared between the study treatments by analysis of variance (ANOVA) including subject, treatment, and sequence effects in the model. Statistical significance will be tested at the 0.05 level (2-sided):

- AUC_{0-t} (Area under the concentration-time curve up to the time of the last quantifiable concentration)
- $AUC_{0-\infty}$ (Area under the concentration-time curve extrapolated to infinity)
- C_{max}
- t_{max}

• t_{1/2}

AUC_{0-t}, AUC_{0- ∞} and C_{max} will present estimates of extent and rate of absorption. t_{max} will be compared between treatments using the Wilcoxon-Singed Ranks test.

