8. TREATMENT OF SUBJECTS

8.1. Methods of Assigning Subjects in Part 1

Subject treatment assignment will be based on a generated randomization scheme with a ratio of 1:1 (test: reference). Each treatment group will have 16 subjects randomized to receive either test drug or reference drug.

8.2 Methods of Assigning Subjects in Part 2

All subjects who have completed Part 1 will be rolled over to Part 2 after a wash-out period for at least 14 days since the last dosing to assess food effect on the PK profile of levamlodipine maleate tablets. Subjects will receive a single oral administration of study drug under a high-fat /

high-calorie meal. This meal should derive approximately 150, 250 and 500-600 calories from protein, carbohydrate and fat, respectively.

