11.1.5. Clinical Laboratory Assessments

Hematology, blood chemistry, and urinalysis evaluations will be performed at screening and few other visits. The list of clinical laboratory assessments is included in Appendix A. Subjects should be fasted overnight prior to blood sample collection for safety tests.

The total volume of blood collected for safety laboratory assessments will be approximately 70 mL.

The results of clinical laboratory tests conducted at the screening visit must be assessed by the Investigator to determine each subject's eligibility for participation in the study. The Investigator should signify review of the laboratory reports by signing and dating the report. If subjects' values are out of range and the Investigator deems the out of range value is clinically significant, the Investigator must discuss and agree upon individual cases with CSPC Pharma's Medical Monitor prior to enrollment.

Any significant abnormalities should be fully investigated. Whenever possible, the etiology of the abnormal findings will be documented on the CRF. Laboratory results with clinically significant abnormal values may be repeated for verification. Additional tests and other evaluations required to establish the significance or etiology of an abnormal result or to monitor the course of an AE should be obtained when clinically indicated. In particular, if a clinically significant abnormal result is observed that is not resolved by the final study visit, repeat tests will be performed if possible and resolution or stability of the abnormality will be recorded in the source documentation.

Any clinically significant laboratory abnormalities that are either serious (e.g., require medical intervention or result hospital admission) or unexpected will be promptly reported to the CSPC Pharma's representative. Any additional relevant laboratory results obtained by the Investigator during the course of this study will be reported to CSPC Pharma.

Virus serology (HIV, and hepatitis B and C) will be assessed at the screening visit only, and must be negative to qualify enrollment.

Drug and alcohol tests will be conducted at the screening visit and on Day -1. Results must be negative to qualify enrollment prior to dosing.

Serum pregnancy test will be performed at screening visit, and urine pregnancy test on Day -1 for female subjects only.

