15.1. Ethics Review

The Investigator (or designee) must submit this study protocol, the CSPC Pharma approved ICF, patient information sheets (PISs), subject recruitment materials, and other appropriated documents to the appropriate IRB or IEC, and following review of the submitted materials is required to forward to CSPC Pharma (or designee) a copy of the written and dated approval/favorable opinion signed by the Chairman, along with a list of the IRB/IEC composition.

The approval/favorable opinion should clearly state the trial (study number, protocol title, and version number), the documents reviewed (Protocol, ICF, IB, etc) and the date of the review. The study will not commence at the study site until CSPC Pharma has received a copy of this written and dated approval/favorable opinion.

During the trial, any amendment to the protocol and the ICF (as appropriate) should be submitted to the IRB/IEC. The IRB/IEC should also be informed of any event likely to affect the safety of subjects or the continued conduct of the trial, in particular any change in safety. Additionally, all updates to the IB will be sent to the IRB/IEC. A progress report will be sent to the IRB/IEC and the protocol will be reviewed annually (e.g., re-approved) or more frequently, as required by IRB/IEC or local regulations.

The Investigator will notify the IRB/IEC of the conclusion of the clinical study within 1 month of completion or termination of the study. The final report sent to the IRB/IEC will also be sent to CSPC Pharma, along with the completed CRFs and all necessary regulatory documents, thereby fulfilling the Investigator's regulatory responsibility.

The Investigator will maintain a copy of all correspondence with the IRB/IEC, including copies of approved documents. The Investigator will also maintain a copy of the IRB/IEC membership list, including members' occupation and qualifications (or a statement confirming compliance with GCP requirements for committee composition). An IRB or IEC General Assurance Number may be accepted in lieu of a membership roster.

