2.3 Study Periods, Visit, and Day

The overall study consists of initial screening and three treatment periods, separated by two wash-out periods between treatment periods. Each treatment period includes a 3-day visit admitted in the CRU, followed by 5 daily visits. A reference date refers to the start date of the study drug administration for each treatment period. All efficacy and safety assessments at all visits will be assigned a day relative to this date within each treatment period. The relative day will be defined as: visit date – reference date + 1 for visits on or after the reference date, and visit date – reference date for visits before the reference date. Consequently there is no 'Day 0' defined.

In general, the baseline is defined as the last assessment before the intake of the first study medication during each treatment period unless specifically stated otherwise. All scheduled assessments after first administration of study drug will be used. Repeat/unscheduled assessments will not be used in descriptive statistics or any per-time point analysis, but will be shown in listings as applicable. Pre-dose unscheduled assessments will be taken into account for baseline determination and post first dose unscheduled assessments will be taken into account for worst-case determination as applicable.

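### Section 10.1 bases each subject's PK blood volume on 16 samples (about 100 mL), but the schedule has 23 per dosing and three dosings: 69 samples, or about 414 mL at the stated 6 mL

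*Protocol*

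**What the plan says.** Protocol section 10.1 opens with the sampling schedule: "A total of 23 blood samples will be collected at the following time points", followed by one pre-dose and 22 post-dose times running to 168 hours, to be repeated at each dosing. Its next paragraph states: "Total volume of blood collected for determination of study drug concentration will be approximately 100 mL". The bracket after that figure shows its derivation, 16 × 6 mL, and the sentence applies it to each subject.

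The number of dosings is clear elsewhere. Section 7.2 repeats the Period One procedures in Period Two, and section 8.2 says "All subjects who have completed Part 1 will be rolled over to Part 2". SAP section 2.3 confirms it: "The overall study consists of initial screening and three treatment periods, separated by two wash-out periods between treatment periods".

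Two further statements bear on the volume. Section 10 leaves sample handling to another document: "Guidelines for preparing, labeling, storing and shipping plasma samples for bioanalytical analyses will be provided in a separate manual". Section 11.1.5 gives the other blood volume in the protocol: "The total volume of blood collected for safety laboratory assessments will be approximately 70 mL".

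**The concern.** The multiplier of 16 contradicts the count of 23 in the paragraph directly above it, and it takes no account of the second and third dosings. The result is described as a total for each subject, so a reader would take about 100 mL as the whole PK blood requirement.

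What is at stake is the accuracy of the stated burden. Section 15.1 sends this document for ethics review ("The Investigator (or designee) must submit this study protocol"), and this is the only PK blood volume it contains. A committee relying on it would see a figure below one period's requirement at the protocol's own 6 mL, and about a quarter of what a completer would give. The bioequivalence comparison, the food-effect comparison and the sampling times are untouched.

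**Working it through.** **Inputs**

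- Samples per dosing: 1 pre-dose plus 22 post-dose (1 to 12 hourly, then 14, 16, 24, 36, 48, 72, 96, 120, 144 and 168 h) = 23. The same list appears in the synopsis, the footnotes to Tables 5-1, 5-2 and 5-3, and sections 7.1.3, 7.2.2, 7.3.2 and 10.1.
- Dosings per completer: Part 1 Period 1, Part 1 Period 2 and Part 2 = 3.
- Volume per sample: 6 mL, found only in the bracket in section 10.1.

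**The plan's own figure.** 16 × 6 = 96 mL, which the text rounds to about 100 mL. The product is right; the factor of 16 is not supported by any schedule.

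**Sample count, independent of draw volume**

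- One period: 23 / 16 = 1.44.
- Completer: 23 × 3 = 69 samples; 69 / 16 = 4.31, so 16 is 23% of the scheduled number.

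**Volume = samples × 6 mL**

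| Scope | Samples | Volume at 6 mL | Ratio to 96 mL |
|---|---|---|---|
| One period | 23 | 138 mL | 1.44 |
| Part 1 (two periods) | 46 | 276 mL | 2.88 |
| Both parts (three periods) | 69 | 414 mL | 4.31 |

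**Draw volume at which 100 mL would be right**

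- One period: 100 / 23 = 4.35 mL.
- Part 1: 100 / 46 = 2.17 mL.
- All three periods: 100 / 69 = 1.45 mL.

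None of these is 6 mL.

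**Sensitivity for a completer.** The documents give no draw volume other than 6 mL, so the lower values are assumptions: 69 samples take 138 mL at 2 mL, 207 at 3 mL, 276 at 4 mL, 345 at 5 mL and 414 at 6 mL. All exceed 100 mL.

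**With safety bloods (context only).** Safety tests are scheduled at screening and on Day 0 and Day 8 of three periods, which is 1 + 2 × 3 = 7 draws; 70 / 7 = 10 mL each. That makes it plausible, but not certain, that the 70 mL covers the whole study. If it does, and 6 mL is right, the combined volume is 414 + 70 = 484 mL, against 100 + 70 = 170 mL from the two stated figures. The period concerned is given in the synopsis: "The total duration of the study for each completed subject is about 2 months", including screening. Discard volume and repeat samples are not counted.

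**The case against.** Section 10.1 already uses the word total for a single dosing when it gives the 23 samples, so its total volume may also have been meant per dosing. That would reduce the discrepancy to 96 against 138 mL. It would not remove it, because 16 is still not 23, and the sentence refers to each subject. Counting from pre-dose to 24 hours does give 16 time points, but nothing limits the figure to that window and sampling runs to 168 hours.

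The 6 mL is the weaker input. It appears once, beside the faulty multiplier, and could be a tube size rather than a volume drawn. This objection stands against the millilitre totals, which are conditional. It does not touch the count.

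The 484 mL figure rests on further assumptions and is not needed to show the error. Nor is section 11.1.5 shown to be wrong: 70 mL fits seven draws of 10 mL, so clarifying its scope would be an improvement rather than a correction.

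Finally, the schedule itself is stated correctly throughout. Site staff would collect the right samples, and the ethics committee receives that schedule too. This limits the consequence, but a reader would have to redo the multiplication to see that the stated volume is wrong.

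**Conclusion.** The concern holds. The 16 in section 10.1 conflicts with the protocol's own schedule on any reading: it is too low by a factor of 1.4 for one period and 4.3 for a subject completing both parts. These ratios need only the listed time points and the three dosings. At the stated 6 mL, the PK volume is 138 mL per period and about 414 mL per completer instead of about 100 mL; these totals assume 6 mL is the volume drawn. The figure should be corrected because it is a stated subject burden, but the error has no bearing on the trial's statistical conclusions.

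**What to change.** In section 10.1, reconcile the number of samples, the volume per draw and the number of periods, then restate both totals. If 6 mL is confirmed, these are 23 × 6 = 138 mL per period and 69 × 6 = about 414 mL for a subject completing both parts. Otherwise they are 23 and 69 times the actual draw volume. Say explicitly which total is per period and which is per subject, and check any other study document that states a blood volume against the corrected figure.

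While the text is open, it would help to say in section 11.1.5 whether the 70 mL covers the whole study, and to give one combined total per subject.

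The cost is a wording correction and a cross-check. The stated burden becomes less favourable, which may prompt a question from the ethics committee. Subjects, samples and analyses stay as planned.

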10.2. Sample Storage and Shipping

All blood samples will be stored on ice or at 4°C for no more than 30 minutes until plasma is harvested. Blood samples will be centrifuged in a refrigerated centrifuge (approximately 4°C) at ~2000 g for 10 minutes. The harvested plasma will be split into two approximately equal aliquots and stored in 2 mL or appropriate size cryovial tubes. The plasma samples will be frozen within approximately 60 minutes of harvesting and stored at -70°C or -80°C pending shipment for drug analysis.

10.3. Specimen Labeling

Labels will be affixed to the cryovial and polypropylene tubes in a manner that will prevent the label from being detached or smeared after being wet or freezing. The tube labels will follow the instruction to be provided in the PK Lab Manual.

The site will provide a sample inventory page, listing the information above for each sample. The sample inventory page will also include the treatment and study part/period for each series of tubes.

10.4. Sample Shipping Instructions

All plasma samples will be kept frozen and shipped on dry ice by the same day or overnight courier to the designated laboratory.

Plasma samples will be sent to the designated laboratory in two separate shipments. The first shipment of samples (the primary aliquot of each sample) will be shipped based on the schedule specified in the PK Lab Manual. The second aliquot of each sample will be shipped after notification from the designated laboratory.

10.5. Bioanalytical Methodology

Plasma samples will be analyzed by the designated bioanalytical lab using validated methods of liquid chromatographic separation with tandem mass spectrometric detection (LC-MS/MS) for concentrations of (S)amlodipine and (R)amlodipine.

10.6. PK Parameters

The plasma concentration time data for (S)amlodipine and (R)amlodipine will be analyzed using non-compartmental methods. Actual dosing and sampling times will be used for analyses. The

primary PK parameters of interest are: C_{max} , t_{max} , t_{lag} , $t_{1/2}$, λ_z , MRT_{inf}, AUC_{last}, AUC_{inf}, AUC_{extrap}, Cl/F and V_d/f. Additional parameters may be estimated and reported, as appropriate.

11. ASSESSMENT OF SAFETY

For specific timing of assessments, please see Table 5-1, Table 5-2, Table 5-3 for Schedule of Procedures.

11.1.1. Medical History

Demographic characteristics (age, sex, race and ethnicity) will be collected at screening visit. Medical history will be reviewed and collected at screening visit.

11.1.2. Vital Signs

Vital signs, including blood pressure, pulse rate, respiratory rate, and oral temperature, will be measured at the screening and other visits. Subjects should be resting for at least 5 minutes prior to measurement. Vital signs will be measured in sitting position.

Vital signs may be repeated for clinically significant abnormal vital signs at the discretion of the Investigator.

11.1.3. Physical Examination

Physical examinations will be performed by qualified personnel at the screening and few other visits. At the screening visit, height (centimeters) and weight (kilograms) will be measured and BMI will be calculated. All abnormal findings will be documented in the source documentation and the CRF.

11.1.4. Electrocardiogram

Standard resting 12-lead ECGs will be performed at multiple visits. All ECGs will be performed after the subject has rested for at least 5 minutes.

At baseline, three ECGs will be recorded with approximately 3-min interval. The means of the three ECGs will be used as baselines.

Multiple parameters such as HR, PR, RR, QRS, QT and QTcB or QTcF will be measured.

Post-dose ECGs must be evaluated for safety by the Investigator or his/her designee. The final conduction intervals entered into the CRF will be those generated by the ECG machine, unless deemed significantly inaccurate by the review performed by the Investigator or designee. In these cases, the over-read intervals will be documented in the CRF. The Investigator will also record an overall assessment of the ECG. Clinically significant abnormal ECGs may be repeated at the discretion of the Investigator.

11.1.5. Clinical Laboratory Assessments

Hematology, blood chemistry, and urinalysis evaluations will be performed at screening and few other visits. The list of clinical laboratory assessments is included in Appendix A. Subjects should be fasted overnight prior to blood sample collection for safety tests.

The total volume of blood collected for safety laboratory assessments will be approximately 70 mL.

The results of clinical laboratory tests conducted at the screening visit must be assessed by the Investigator to determine each subject's eligibility for participation in the study. The Investigator should signify review of the laboratory reports by signing and dating the report. If subjects' values are out of range and the Investigator deems the out of range value is clinically significant, the Investigator must discuss and agree upon individual cases with CSPC Pharma's Medical Monitor prior to enrollment.

Any significant abnormalities should be fully investigated. Whenever possible, the etiology of the abnormal findings will be documented on the CRF. Laboratory results with clinically significant abnormal values may be repeated for verification. Additional tests and other evaluations required to establish the significance or etiology of an abnormal result or to monitor the course of an AE should be obtained when clinically indicated. In particular, if a clinically significant abnormal result is observed that is not resolved by the final study visit, repeat tests will be performed if possible and resolution or stability of the abnormality will be recorded in the source documentation.

Any clinically significant laboratory abnormalities that are either serious (e.g., require medical intervention or result hospital admission) or unexpected will be promptly reported to the CSPC Pharma's representative. Any additional relevant laboratory results obtained by the Investigator during the course of this study will be reported to CSPC Pharma.

Virus serology (HIV, and hepatitis B and C) will be assessed at the screening visit only, and must be negative to qualify enrollment.

Drug and alcohol tests will be conducted at the screening visit and on Day -1. Results must be negative to qualify enrollment prior to dosing.

Serum pregnancy test will be performed at screening visit, and urine pregnancy test on Day -1 for female subjects only.

